ID: 2018ZY008-CTN

Research name:

*Electroacupuncture Therapy for Change of Pain in
Classical Trigeminal Neuralgia*

Date: June 20, 2018

Electroacupuncture Therapy for Change of Pain in Classical Trigeminal Neuralgia

Study Protocol

Part1. Study objectives

1. To observe the therapeutic effect and safety of electroacupuncture (EA) in the treatment of classical trigeminal neuralgia (CTN).
2. To evaluate whether EA has the advantage over carbamazepine in the immediate effect, long-term effect and post effect of the analgesia in CTN.
3. To demonstrate whether EA has a synergistic effect with carbamazepine on the treatment of CTN, or even whether EA has an alternative effect on carbamazepine.
4. To establish a standardized, effective and convenient therapy program of EA to promote it widely.

Part2. Study program

1. Study subjects

1.1 Source of cases

It is expected that during the four years from January 2018 to December 2021, 120 patients with CTN will be recruited in the Third Affiliated Hospital of Zhejiang Chinese Medical University and Jiaying TCM Hospital.

1.2 Diagnostic criteria

The diagnostic criteria are followed by *The international classification of headache disorders, 3rd edition (beta version)*. *Cephalalgia*. 2013;33(9):629–808, which was published by the headache classification committee of the International Headache Society (IHS) in 2013.

- 1) Pain of one side face should be conformed to the following criteria 2 and 3, with a paroxysm of at least 3 times.
- 2) Occurring in one or more divisions of the trigeminal nerve, with no radiation beyond the trigeminal distribution.

- 3) Characteristics of pain contain at least 3 of the following 4 characteristics:
 - A. Recurring in paroxysmal attacks lasting from a fraction of a second to 2 minutes.
 - B. Severe intensity.
 - C. Electric shock-like, shooting, stabbing in quality.
 - D. Precipitated by innocuous stimuli to the affected side of the face.
- 4) No neurological impairment.
- 5) Eliminating other disease that would cause the pain.

1.3 Inclusion criteria

- 1) Paroxysm pain involving branches of the 2nd and/or 3rd branch of trigeminal nerve.
- 2) The visual analogue score(VAS) baseline score ≥ 5 points, have a attack more than 3 times a day, at least 4 days a week.
- 3) 18 years \leq age \leq 80 years.
- 4) Clear consciousness, have the ability of pain perception and resolution, can complete the basic communication.
- 5) Signed informed consent and volunteered to participate in this study.

1.4 Exclusion criteria

- 1) Those patients with epilepsy, head injury or other related neurological diseases.
- 2) Patients with serious heart, liver, kidney damage or cognitive impairment, aphasia, mental disorders, or unable to cooperate with the treatment.
- 3) Combined with hypertension but poor control.
- 4) Severe depressive with definitive diagnosis recently.
- 5) Pregnant and lactating patients.
- 6) Installing pacemakers.
- 7) For any other reason that is not suitable for the treatment of EA.

1.5 Removed criteria

The subjects who have entered a group of research but who were met one of the following conditions should be removed:

- 1) Those who do not meet exactly with the inclusion and exclusion criteria of the trial.
- 2) There are obviously adverse reactions during the treatment.

3) The subjects are not treated according to the treatment plan of the group after they have entered.

The removed cases should indicate the reason and retained the original medical records. No participation of statistical analysis of efficacy, but those who have received at least one treatment can participate in analysis of adverse reaction.

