1.6 Shedding criteria

Cases that have been entered but not completed the treatment program should be considered as falling off, Such as the following situations:

- 1) Patient withdraws or has been lost their visit.
- 2) The acupuncture treatment has not reached 80%.
- 3) In the treatment, there are serious adverse reactions or adverse events.

The shedding cases should explain the reasons. If the case has been recorded the baseline data, and received at least one time acupuncture treatment, the results of its final main outcome can be carried out for statistical analysis. The medical records should be retained, while the data should not be carried forward during the follow-up.

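### Protocol 1.5 bars removed patients from efficacy analysis, the SAP's FAS keeps every randomised and treated patient, and nothing says which rule prevails

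*Combined protocol and SAP*

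**What the plan says.** **Protocol Part 2, 1.5 (Removed criteria)** covers patients who have already entered a group. The three grounds are ineligibility ("Those who do not meet exactly with the inclusion and exclusion criteria of the trial"), adverse reactions ("There are obviously adverse reactions during the treatment") and off-plan treatment ("The subjects are not treated according to the treatment plan of the group after they have entered"). The consequence is: "No participation of statistical analysis of efficacy, but those who have received at least one treatment can participate in analysis of adverse reaction". A reason for removal must be given.

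**Protocol Part 2, 1.6 (Shedding criteria)** covers patients who do not complete treatment. Its grounds include "The acupuncture treatment has not reached 80" per cent, and "In the treatment, there are serious adverse reactions or adverse events". If a baseline was recorded and at least one acupuncture treatment given, "the results of its final main outcome can be carried out for statistical analysis". The section ends by saying that "the data should not be carried forward during the follow-up".

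**SAP 2.1 (Analysis data set)** defines the FAS as all randomised patients treated at least once, with LOCF for missing values of the main outcome. The PPS holds eligible, compliant patients who took no prohibited drug and completed treatment and the main outcome.

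**SAP 2.2** requires the main outcomes to be analysed by PP and ITT together (item 4) and losses to be compared across the four groups (item 1). Neither item mentions removals under 1.5.

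**The concern.** The population for the main efficacy analysis is not fixed. An analyst could leave removed patients out and cite protocol 1.5, or keep them in and cite SAP 2.1. Either choice would comply with one of the texts.

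The choice matters because grounds 2 and 3 of 1.5 are events after randomisation. Adverse reactions and departures from the plan can depend on the assigned treatment. Scheduled carbamazepine is given in two of the four arms, so reactions to it may be more frequent there. The contrast is not absolute, since protocol 2.5 allows emergency carbamazepine without restriction by arm. If removal differs by arm and removed patients differ in outcome from those who stay, the remaining groups are no longer the groups that were randomised. An analysis reported as ITT would then lack the protection its name implies.

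Ground 1 is different. For ineligible patients the problem shown is only that the two texts disagree.

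**Working it through.** **Step 1. Follow one patient through the text.** Take a randomised patient who has had at least one treatment.

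| Patient | Protocol 1.5 | Protocol 1.6 | FAS, SAP 2.1 |
|---|---|---|---|
| Found ineligible after entry | Out of efficacy | Not a listed ground | In |
| Obvious but not serious reaction, treatment completed | Out of efficacy | Not a listed ground | In |
| Serious adverse reaction | Out, if also obvious | Outcome may be analysed | In |
| Under 80% of acupuncture sessions | Out, if read as off-plan | Outcome may be analysed | In |
| Other off-plan treatment | Out of efficacy | Depends on completion | In |

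Every row is in the FAS under SAP 2.1, and every row is or can be out of efficacy under 1.5. Rows 3 and 4 also set 1.5 against 1.6. The conflict concerns treated patients only, because untreated ones are outside the FAS anyway.

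**Step 2. Look for a rule of precedence.** Section 1.5 refers to no analysis set. SAP 2.1 and 2.2 do not refer to 1.5 or 1.6. ITT appears in SAP 2.2(4) without a definition, and the FAS is the only defined efficacy set besides the PPS. No rule of precedence was found.

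**Step 3. Look for a missing-data rule.** SAP 2.1 carries the last value forward for the main outcome, and one main outcome is the change in VAS at 6 months (protocol 2.6(1)). The last clause of 1.6 can be read as forbidding this for shedding cases. It can also be read as ending data collection, since 1.6 allows the final main outcome to be analysed. The clause is ambiguous.

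**Step 4. What the documents allow on size.** Protocol 2.1 raises 24 per group to 30, and 24/(1 − 0.20) = 30 reproduces this. The allowance is 30 − 24 = 6 per group. Removals under 1.5 would use it up; under the SAP's FAS they would not. At 24 rather than 30 per group the standard error is larger by √(30/24) = 1.118, or about 12%.

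For the estimate itself, let p be the fraction removed in an arm, R the 6-month mean of retained patients and L the mean last value of removed patients. Then:

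- arm mean under 1.5 = R
- arm mean under FAS with LOCF = (1 − p)R + pL = R + p(L − R)
- difference between the two rules, for arm 1 against arm 0 = p₁g₁ − p₀g₀, where g = L − R

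The documents give no value of p or g. Purely as an assumption, take 3 or 6 of 30 removed in one arm, none in the other, and a gap of 1 or 2 points. The rules then differ by 0.10 × 1 = 0.1 up to 0.20 × 2 = 0.4 VAS points, with either sign. In a factorial main effect, which averages two arms, a shift in one arm is halved, to 0.05 to 0.2. With equal removal and equal gaps the difference is 0.

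**The case against.** The best defence is that 1.5 was meant to describe the PPS. Its grounds 1 and 3 parallel the PPS conditions on eligibility and adherence, and applying the bar to both sets would leave the ITT analysis little purpose. As a guess at intent this is reasonable, but it is not in the text. Section 1.5 speaks of efficacy without limit. Section 1.6 also tells against it: shedding cases have not completed treatment and so fail the PPS too, yet their outcome may be analysed. If 1.5 concerned only the PPS, the distinction between removed and shedding cases would do no work for efficacy.

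Some safeguards exist. Reasons for removal are recorded, patients are blinded and record side effects daily, and SAP 2.2(1) compares losses, including those due to adverse events. These help in detecting a problem, but they do not settle who is analysed.

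A reader might infer more than the documents support:

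- **That patients who take analgesics for pain would be removed, mostly from the less effective arms.** Protocol 2.5 permits emergency carbamazepine and asks that other analgesic measures be recorded; it does not order removal. Prohibited drugs appear as a PPS condition, not as a ground in 1.5.
- **That an unblinded acupuncturist could steer removals for drug reactions.** Protocol 2.3 ties the lack of blinding to the needling. The placebo tablets match carbamazepine in appearance (protocol 2.4), and nothing says that the acupuncturist knows the drug allocation or decides removals.
- **That the carry-forward clause flatly contradicts LOCF.** The reading in step 3 that ends data collection is available, so this is a request for clarification.

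**Conclusion.** The concern holds as a contradiction in the text. Treated patients who meet 1.5 are barred from efficacy analysis by the protocol and included by the SAP's FAS, and some of them are also covered by the permissive rule in 1.6. No precedence is stated. This finding rests on the wording alone and needs no assumption about data.

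The statistical consequence is conditional. If 1.5 were applied to the FAS, patients would be excluded for post-randomisation events, and the comparison would be biased if removal and outcome differ by arm. A reader might infer a bias of known size, or one that favours electroacupuncture. The documents support neither: they give no removal rates and no outcomes for removed patients. The 0.1 to 0.4 points above rest on assumed inputs and measure the gap between two rules, not the error of either. They should not be set against differences between pairs of the assumed group means, because protocol 2.1 does not name the contrast behind the sample size.

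**What to change.** 1. **Protocol 1.5:** limit the bar on efficacy analysis to the PPS.
2. **SAP 2.1 and 2.2:** state that every randomised patient with at least one treatment stays in the FAS in the assigned group, and that ITT means this FAS. If ineligible patients are to be an exception, write it in SAP 2.1 and have it decided without knowledge of the group.
3. **Protocol 1.5 and 1.6:** give each case that meets both sections one analysis status.
4. **Protocol 1.6 and SAP 2.1:** state one missing-data rule for the 6-month VAS, in the same terms in both places.
5. **SAP 2.2(1):** report removals under 1.5, with reasons, by group.

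The cost is wording changes in four sections and slightly more analysis work, with no extra patients or visits. Continuing the scheduled diaries after removal, where the patient agrees, would reduce missing data (at most 4 + 2 + 2 = 8 diary-weeks per patient). It is optional, and the contradiction can be resolved without it. The changes should be made before anyone analysing the data knows the groups.

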2.1 Analysis data set

(1) Full Analysis Set (FAS):

A collection of all randomly assigned and at least one treated case. When analyzing the main therapeutic indicators, the missing values in the FAS set were

transferred to the current (LOCF) method by using the results observed at the latest time point. The Available Case Analysis principle was used in the Analysis of secondary efficacy indicators, general conditions and safety Analysis.

(2) Per Protocol Set (PPS):

Compliance set refers to meet the inclusion criteria and follow the test protocol to complete the treatment of the set of cases, which is consistent with the test protocol, compliance, did not take prohibited drugs, to complete the evaluation of effectiveness (at least the main outcome) cases.

(3) Security Analysis System (SAS):

At least one treatment is received and the actual data of the safety indicator evaluation record is available.

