2.2 Statistical analysis content

The main analysis contents include:

(1) Four groups of cases distribution: Four groups of the total loss rate and the loss due to adverse events off rate comparison.

(2) Comparability analysis: Compare demographic data and other baseline values to measure the comparability of the four groups.

(3) Compliance analysis: The four groups of patients were compared according to the amount of time to receive the appropriate treatment, the program did not use prohibited drugs.

(4) Effectiveness analysis: Main therapeutic indexes are analyzed by PP and ITT simultaneously. Since this study is a multi-center clinical trial, the effect of the central effect and baseline on the therapeutic effect should be taken into account in the analysis.

(5) Effect factor analysis: such as age, gender, duration, combined medication and other factors on the efficacy.

(6) Safety analysis: First, according to the requirements of adverse reaction correlation list describes four groups of adverse events and adverse reactions (including the number of cases of adverse events and laboratory examination indexes before and after the test "normal turn abnormal cases and different rate), statistical

analysis of the adverse reactions by chi-square test.

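### Protocol 1.5 bars randomised, treated patients from efficacy analysis while the SAP's FAS keeps them, and no order of precedence is stated

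*Combined protocol and SAP*

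**What the plan says.** Protocol Part 2, section 1.5, applies to patients who have already entered a group. It lists three grounds for removal:

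- not meeting the eligibility criteria;
- an adverse reaction: "There are obviously adverse reactions during the treatment";
- off-plan treatment: "The subjects are not treated according to the treatment plan of the group after they have entered".

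The consequence is in its closing paragraph: "No participation of statistical analysis of efficacy, but those who have received at least one treatment can participate in analysis of adverse reaction". The threshold for an obvious reaction is not defined.

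Section 1.6 (Shedding criteria) deals with patients who do not complete the programme. Its examples are withdrawal or loss to follow-up, less than 80% of the acupuncture, and "In the treatment, there are serious adverse reactions or adverse events". If such a patient has a baseline and at least one acupuncture treatment, "the results of its final main outcome can be carried out for statistical analysis".

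SAP 2.1 defines the FAS as "A collection of all randomly assigned and at least one treated case", with no exception for cases removed under 1.5. It describes the PPS as follows: "Compliance set refers to meet the inclusion criteria and follow the test protocol to complete the treatment of the set of cases". The PPS definition has no adverse-reaction exclusion. SAP 2.2(4) adds: "Main therapeutic indexes are analyzed by PP and ITT simultaneously".

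**The concern.** For a patient who was randomised, treated at least once and then removed under 1.5, the protocol says not to analyse efficacy and the SAP says to analyse it. Both cannot be followed, and neither document gives precedence.

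Two of the three grounds arise after randomisation and may be consequences of treatment. The arms differ in ways that could produce different rates. Carbamazepine has its own list of expected reactions (protocol 2.6(4)). Sham needling is shallower and carries no current (protocol 2.4). Excluding on these grounds can break the comparability that randomisation gave.

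The ITT analysis is also meant to stand beside the PP analysis as a check on it. Under 1.5 as written the same patients leave both, so the check is lost for exactly the patients where it matters. With the rule unresolved, the choice could be made after the data are seen.

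**Working it through.** **Step 1. Set the rules side by side for treated, randomised patients.** SAP 2.2(4) does not tie ITT to a named set; I take it to mean the FAS.

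| Patient | Protocol 1.5 | Protocol 1.6 | FAS |
|---|---|---|---|
| Ineligible, found after entry | barred | not addressed | in |
| Obvious, non-serious reaction, completes | barred | does not apply | in |
| Serious reaction, does not complete | barred, if the reaction also counts as obvious | may be analysed | in |
| Under 80% of acupuncture | barred, if read as off plan | may be analysed | in |
| Off plan in another way, completes | barred | does not apply | in |

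The conflict between 1.5 and the FAS appears in every row. The conflict with 1.6 appears only in the third and fourth rows, and there 1.6 is permissive.

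**Step 2. Size of one exclusion.** Protocol 2.1 plans 30 patients per arm, so each exclusion is 1/30 = 3.3% of an arm.

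**Step 3. Shift in an arm mean.** Let k of 30 patients be excluded, with mean VAS outcome d points away from the remaining patients, whose mean is m. The full-arm mean is [(30 − k)m + k(m + d)]/30 = m + kd/30. Exclusion therefore shifts the arm mean by (k/30) × d. The documents give neither k nor d. I assume k = 1, 3, 6 in one arm only and d = 1 to 3:

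| k | d = 1 | d = 2 | d = 3 |
|---|---|---|---|
| 1 | 0.03 | 0.07 | 0.10 |
| 3 | 0.10 | 0.20 | 0.30 |
| 6 | 0.20 | 0.40 | 0.60 |

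**Step 4. Yardstick.** Protocol 2.1 gives planning means of 5.23 (EA + carbamazepine), 4.45 (EA + placebo), 5.50 (sham EA + carbamazepine) and 0.00 (sham EA + placebo). Taken at face value:

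- EA main effect = (5.23 + 4.45)/2 − (5.50 + 0.00)/2 = 4.84 − 2.75 = 2.09
- Carbamazepine main effect = (5.23 + 5.50)/2 − (4.45 + 0.00)/2 = 5.365 − 2.225 = 3.14

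**Step 5. Effect on the main effects at d = 2.** Each main effect averages two arms on each side, so a shift in one arm moves it by half.

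| k | Shift in main effect | Share of EA effect (2.09) | Share of carbamazepine effect (3.14) |
|---|---|---|---|
| 1 | 0.067/2 = 0.033 | 2% | 1% |
| 3 | 0.20/2 = 0.10 | 5% | 3% |
| 6 | 0.40/2 = 0.20 | 10% | 6% |

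In a comparison of two arms, the bias is zero if k and d are the same in both. It is also zero if 1.5 is not applied to the FAS.

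**The case against.** The best defence is that 1.5 was meant as a per-protocol rule. Its eligibility and off-plan grounds closely match the PPS conditions, and SAP 2.1 is the place that defines who is analysed. A statistician who follows the SAP excludes no treated patient, and the bias does not arise. This is plausible, but neither document says it. The bar in 1.5 covers efficacy analysis without limit, and its adverse-reaction ground has no counterpart in the PPS definition. What stands is that the bias is conditional on 1.5 being applied as written.

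A reader might also infer several stronger points that the documents do not support:

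- **That 1.6 retains the same patients whom 1.5 bars.** It covers only non-completers and says only that their outcome may be analysed. The overlap is partial.
- **That an unblinded physician decides who is removed.** The acupuncture physician records adverse events (protocol 2.6(4)) and the doctors are not blinded (protocol 2.3). But patients, who are to be blinded, also record side effects in the daily diary (protocol 2.6), and no one is named as deciding a removal.
- **That the shift could reach half of the planned effect.** Measured against the gap between EA + carbamazepine and EA + placebo (5.23 − 4.45 = 0.78), the d = 2 shifts are 9%, 26% and 51%. Protocol 2.1 sizes a factorial design and never names that pair as its target. The main-effect shares are the fairer measure.
- **That safety data are lost.** Removed patients treated at least once may stay in the adverse-reaction analysis.

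**Conclusion.** The point stands as a direct conflict between protocol 1.5 and the FAS in SAP 2.1, with a partial overlap from 1.6 and no stated precedence. Confidence in the textual conflict is high.

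That bias will occur is not established. It needs 1.5 to be applied to the ITT analysis and the exclusions to differ between arms in number or in outcome. Its direction depends on the sign of d. On the assumptions above (one arm only, d = 2), the EA main effect moves by about 2% to 10%. The upper end requires 6 of 30 patients to be excluded from one arm and none elsewhere, which is an extreme case.

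This should be fixed: the rule decides who enters the main efficacy analysis, and as written it undermines the planned ITT analysis.

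**What to change.** Replace the closing bar of protocol 1.5 with wording such as:

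> All randomised cases treated at least once stay in the FAS for efficacy, whatever the reason for removal; the SAP analysis-set definitions take precedence over 1.5. Ineligible or off-plan cases are excluded from the PPS only; an adverse reaction alone does not exclude a case that otherwise meets the PPS definition.

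The last clause is needed. Simply sending all removed cases out of the PPS would newly exclude a patient who has an obvious reaction but completes on protocol, which the SAP's PPS definition does not do. The present provision that treated removals may enter the adverse-reaction analysis should be kept.

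The cost is a few sentences of amendment. No extra patients, visits or procedures are needed, because both analysis sets and the pain diaries to 6 months are already planned.

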1.6 Shedding criteria

Cases that have been entered but not completed the treatment program should be considered as falling off, Such as the following situations:

- 1) Patient withdraws or has been lost their visit.
- 2) The acupuncture treatment has not reached 80%.
- 3) In the treatment, there are serious adverse reactions or adverse events.

The shedding cases should explain the reasons. If the case has been recorded the baseline data, and received at least one time acupuncture treatment, the results of its final main outcome can be carried out for statistical analysis. The medical records should be retained, while the data should not be carried forward during the follow-up.

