2.1 Sample size estimation

The glmpower process of SAS9.3 software is applied to estimate the sample size. According to the literature and the preliminary experiment, the mean values of the

VAS score of EA+Carbamazepine group, EA+Placebo group, sham EA+Carbamazepine group, sham EA+Placebo group were 5.23,4.45,5.50,0.00. The standard deviation was 1.6. Under the condition of $\alpha=0.05$, the test efficiency $1-\beta=0.8$, the four groups were allocated with the 1:1:1:1 proportion, the sample size of each group was calculated at least 24. Considering the existence of shedding and other factors, in the premise of guaranteeing the minimum sample size, the sample size was enlarged by 20% to 30 cases in one group, in total 120 cases for 4 groups. Because of the complexity of the sample calculation process of factorial design, the formula is not listed here.

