disinfection of the facial skin. The superficial acupuncture will be applied for local points. The tiny needles (0.18×25 mm) will be selected to stimulate the local points with shallow row needling according to the distribution of neuropathy branch of trigeminal neuralgia. The technique should be lightly, the depth should be within 5 mm. It is not required a sense of “Qi” and should not touch the trigger point (the trigger points are the pain sensitive places that light touch can trigger severe pain, such as tiff, cheek, nose and so on. The doctor should have a communication with the subject before needling to clear the position of the trigger, do not needle or touch it.) The He-gu (LI4) and Wai-guan (SJ5) points will be selected as the distal points stimulating with 0.25×40mm needle (20-30mm depth). After the subject has a sense of acid distention (“get Qi”), the reducing method of twirling and lifting-inserting will be applied 10 times. If the subject is feeling pain seriously, the distal acupoints can be needling firstly with reducing method sharply until the pain relief. Then it’s turn to needling the local acupoints .

EA parameters: The Xia-guan (ST7) and Quan-liao (SL18) (or Xia-guan (ST7) and Jia-che (ST6)), He-gu (LI4) and Wai-guan (SJ5) acupoints will be received EA treatment by HuaTuo SDZ- II B acupoint neural stimulator. The EA parameter is a dilute wave with 2/100 Hz, the treatment time is 60 minutes and the current intensity is comfortable to subjects.

4) Oral carbamazepine

Carbamazepine tablets (Jiangsu Pengli Pharmaceutical CO., LTD., 0.1g*100 tablets) should be took orally, 0.1g each time, thrice daily.

5) Frequency, duration and time

Treatment will be performed 3 times per week, and 4 weeks of continuous interventions for a total of 12 times.

(2) EA + Placebo group

In this group, the selection, positioning and manipulation of acupoints, the frequency, duration and retaining needle time of treatment are same as EA + Carbamazepine group; placebo, that appearance and specifications are the same as

carbamazepine, are cooperated taken of dose 0.1g, thrice daily.

(3) Sham EA+ Carbamazepine group

Selection of points and locations: the non-meridional points which are means to the points beside 5-10mm of the real acupoints (avoid the trigger point) in the EA group will be selected and needled with more shallow acupuncture (the depth of needling is about 1-2mm).

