2.6 Therapeutic effects indexes

Subjects are required to write a verifiable diary card to record their pain symptoms in 24 hours every day. The diary includes the following items: (1) daily attack frequency (spontaneous and provoking pain frequency); (2) provoking factors; (3) average pain intensity(VAS) in the past 24 hours; (4) side effect in the past 24 hours (including side effect of drugs or acupuncture); (5) Is there another analgesia therapies have been adopt ? Please record it.

(1) Indexes of main outcome evaluation

- 1) Change from Baseline Intensity of Pain at 6 months (evaluation of the pain by VAS with 0-10 points).
- 2) Change from Baseline Brief introduction of 2-week pain.

Evaluation method: According to pain diary, we will take average data of 2 weeks before treatment (-2~0 week) as baseline, 2 weeks of treatment phase (1~2 week) as data of treatment phase I, 4 weeks of treatment phase (3~4 week) as data of treatment phase II. During the follow-up period, the pain diary card will be continued in the 2 weeks before 3 months (11~12 week)/6 months (23~24 week) after treatments.

(2) Indexes of secondary outcome evaluation

- 1) Brief Pain Inventory-Facial scale (BPI-Facial)
- 2) Patient Global Impression of Change (PGIC)
- 3) Short-Form McGill Pain Questionnaire
- 4) Short- Form 36 Questionnaire

(3) Research cycle and evaluation time points

The treatment periods of this research are 4 weeks, and the follow-up period is 6 months. The above indexes are observed at the time points of baseline (the same day with the grouping and treatment for the subject), treatment period I (the end of the 2nd week), treatment period II (the end of the 4th week), follow-up period I (3rd months after treatment) and follow-up period II (6th months after treatment). The main outcome indexes will be measured weekly (1th week to 4th weeks) during the treatment period.

(4) Safety evaluation and acupuncture expectation evaluation

The relevant safety indicators during the treatment period and during the follow-up period are recorded at any time on the subjects' adverse event records, which is recorded by the acupuncture physician.

- 1) Safety evaluation of electric needle:

The abnormal acupuncture should be record, including broken needle, left needle, fainting, unbearable acupuncture pain (VAS \geq 8 points), local hematoma, infection and abscess. And the symptoms, average degree and average duration of other discomfort

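### Patients with fewer than 10 of 12 sessions are classed as drop-outs, and no rule secures or clearly uses their 6-month pain diary

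*Combined protocol and SAP*

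**What the plan says.** Treatment is 12 sessions: "Treatment will be performed 3 times per week, and 4 weeks of continuous interventions for a total of 12 times" (protocol section 2.4). Section 1.6 defines shedding by treatment completion, not by missing data: "Cases that have been entered but not completed the treatment program should be considered as falling off". Its list puts item 2), "The acupuncture treatment has not reached 80" per cent, next to item 1), "Patient withdraws or has been lost their visit", and item 3), serious adverse reactions or events. For a shed patient with baseline data and at least one session, "the results of its final main outcome can be carried out for statistical analysis", but "the data should not be carried forward during the follow-up".

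Other rules reach the same patients:
- Section 1.5 item 3) removes anyone not treated according to the group's treatment plan and excludes them from the efficacy analysis.
- Section 2.8 uses the same 80% cut-off as a compliance criterion.
- SAP section 2.1 puts every randomised patient with at least one treatment in the FAS and fills missing main-outcome values by LOCF. It reserves the PPS for patients who completed treatment to protocol.
- SAP section 2.2 (4) asks for the main outcome by both PP and ITT.

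The first main outcome in section 2.6 is change in VAS pain at 6 months. For follow-up, "the pain diary card will be continued in the 2 weeks before 3 months" and likewise before 6 months (weeks 11–12 and 23–24).

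**The concern.** Missing sessions is incomplete treatment. It is not departure from the study, and a patient who came nine times may be willing to fill in a diary at month 6. Section 1.6 does not make that distinction, and no other section does.

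What is at stake is the randomised comparison at the main time point. Attendance is decided after randomisation and can depend on relief, discomfort and arm. If partial attenders drop out of the month-6 data, the patients left are a selected group. If a treatment-period value stands in for them, the analysis cannot show any fading of effect in these patients between week 4 and month 6, which is what a 6-month outcome is there to detect.

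**Working it through.** **1. Who is affected.** 0.80 × 12 = 9.6, so 10 sessions are needed and nine or fewer means shed. This is settled by the end of week 4, before either follow-up diary window.

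**2. What each rule does with the month-6 value of such a patient.**

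| Rule | Month-6 main outcome |
|---|---|
| Section 1.6 | Final main outcome may be analysed, but nothing is carried into follow-up: missing unless a diary was kept |
| Section 1.5 item 3), if applied | Patient excluded from efficacy analysis |
| SAP section 2.1, FAS | Observed value if there is one; otherwise LOCF |

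These cannot all be followed for one patient. If the last observation dates from week 4, LOCF bridges about 20 weeks (24 − 4, windows counted from the start of treatment) or about 24 weeks (counted from its end).

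**3. The plan's own allowance.** Section 2.1 introduces it with "Considering the existence of shedding and other factors". The step reproduces: 24 / (1 − 0.20) = 30 per arm, so the allowance is 6 per arm and 24 of 120. It covers every cause of loss, so 24 is a ceiling for partial attenders. Whether 24 per arm is itself right is a separate question and is not needed here.

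**4. If the values are simply missing.** Losing the full 20% multiplies the standard error by √(30/24) = 1.118, about 12% more than with 30 per arm. The plan has already budgeted for that, so precision is not the main issue. The documents give no basis for putting a figure on the selection effect.

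**5. If LOCF fills them.**
- Inputs from the plan: SD 1.6, two-sided 0.05, 30 per arm, so the two EA arms against the two sham arms is 60 v 60.
- Assumed: a fraction p of each arm is affected, and these patients have an EA effect of b points during treatment and nil at month 6. SD unchanged; normal approximation.
- Spurious difference = p × b.
- SE = 1.6 × √(2/60) = 0.292.
- False-positive chance = P(|Z + p·b/SE| > 1.96).

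| p | b | Spurious difference | p·b/SE | Chance of p < 0.05 |
|---|---|---|---|---|
| 5% | 1 | 0.05 | 0.17 | 5.3% |
| 5% | 2 | 0.10 | 0.34 | 6.4% |
| 10% | 1 | 0.10 | 0.34 | 6.4% |
| 10% | 2 | 0.20 | 0.68 | 10.5% |
| 20% | 1 | 0.20 | 0.68 | 10.5% |
| 20% | 2 | 0.40 | 1.37 | 28% |

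For scale, the means in section 2.1 put EA + carbamazepine and sham EA + carbamazepine only 5.50 − 5.23 = 0.27 points apart.

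**The case against.** The best defence is that no section stops the diaries. Section 2.6 asks them of subjects generally, with no exception for shed cases; section 2.8 records contact details for follow-up; and the FAS includes everyone treated at least once, with LOCF only for values that are missing. If the diaries were collected, the FAS definition would let them be used. This stands as far as it goes: a reader might infer that the protocol orders follow-up to end below 80%, and the text does not say so. It does not remove the problem. A site that follows section 1.6 records the patient as fallen off and finds no instruction to go on.

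It can also be said that section 1.6, read naturally, forbids carrying a treatment-period value to month 6, so the LOCF figures do not apply. Under section 1.6 alone that is right; they arise only if the SAP rule governs. The two rules conflict, and neither yields an observed month-6 value.

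A third objection is that this only restates a complaint about LOCF. The sizes in the second table are indeed LOCF effects, but a better imputation method would not recover diaries that were never collected.

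Finally, 80% is a reasonable compliance threshold. Agreed: the objection is to its use as a drop-out criterion.

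**Conclusion.** The concern holds as a gap and a conflict between rules. Patients with nine or fewer sessions are classed with withdrawals and losses, three sections treat their main outcome differently, and none secures the month-6 diary. Missing or substituted 6-month values in a group selected after randomisation are the likely result, though this is inferred from the drop-out label and the absence of any instruction to continue.

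Under LOCF the spurious difference is about 0.05–0.4 points and the false-positive chance about 5–28%, on the assumed values above. Two stronger readings should be resisted. The 28% is not an expected error rate: it needs the whole 20% allowance to be partial attenders and a 2-point effect that vanishes completely, and the other scenarios give about 5–10%. Nor does the plan predict 24 such patients, because the allowance also covers withdrawal, loss, serious adverse events and other factors. The change is worth making because it is cheap and protects the main time point.

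**What to change.** By short amendment to the protocol and SAP:
1. Use the 80% attendance cut-off only as a PPS criterion, and take item 2) out of the shedding list in section 1.6.
2. State that missing sessions does not by itself end follow-up; that the weeks 11–12 and 23–24 diaries and the scheduled scales are still collected from patients who consent and can be contacted; and that observed values are used in the FAS.
3. Reconcile section 1.5 item 3), the analysis and carry-forward wording in section 1.6, and the FAS and LOCF text in SAP section 2.1, so that partial attenders are not removed from the FAS and one rule governs any value still missing.

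Section 1.6 item 3) and the adverse-event and termination rules are left as they are by this change. Treatment and sample size do not change. The cost is some extra effort to obtain already scheduled diaries and scales from less motivated patients, at most about 24.
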